6 TREATMENT OF SUBJECTS

6.1 TREATMENT PLAN

6.1.1 Screening/Randomization (Day -30 to Day 0 Pre-Surgery)

Patients will be identified through pre-operative scheduling procedures in advance of their complex cardiac surgery. Patients already hospitalized may be included.

Patients undergoing urgent or emergent cardiac surgery are eligible for the study, subject to institutional review board (IRB) approval of an appropriate informed consent process.

In order to minimize the number of patients who enroll in the study but do not require RBC transfusion, only patients with a relatively high likelihood to receive a transfusion as determined by the Investigator (e.g., patients currently on regimen of aspirin, clopidogrel (or analogs) and/or GPIIb/IIIa inhibitors), or patients with a TRUST score of ≥ 3 will be eligible for enrollment. A TRUST score of ≥ 3 corresponds to a high likelihood of requiring red cell transfusion within 96 hours of surgery. Study consent/assent will be sought in these eligible subjects within 30 days of their surgical procedure. Subjects who consent/assent to the study will be assigned a subject identification (ID) number and undergo screening.

The complete list of screening assessments are outlined in Table 7.1a. Data may be derived from the medical record where performed within 30 days prior to their surgical procedure. Blood samples for determination of HLA antibodies will also be collected at the screening visit and sent for testing at a specialty central laboratory. In certain situations, it is possible for a mobile medical professional, authorized by the sponsor and requested by site personnel, to conduct a home health service visit at a subject's home to collect screening assessments. Patients who fail eligibility for any or multiple inclusion/exclusion criteria may be rescreened for eligibility closer to the time of surgery.

All available components of the TRUST score (age, sex, Hb, weight, type of surgery, serum creatinine, surgical history and surgical task) will be collected on the case report form. The TRUST score (or the minimum and maximum possible TRUST scores, if there are any missing components) will be calculated according to the published algorithm ([APPENDIX 1](#)).

Eligible subjects will be randomized up to 7 days before or on the day of surgery, but prior to the start of surgery (i.e., induction of anesthesia). The adverse event collection period will begin at the beginning of surgery or the first study RBC transfusion, whichever is first.

Cerus Corporation

Title: A Randomized, Double-Blinded, Controlled, Parallel Group, Non-inferiority, Phase III Study to Evaluate the Efficacy and Safety of the INTERCEPT Blood System for Red Blood Cells in Patients undergoing Complex Cardiac Surgery Procedures (the ReCePI study)

For non-transfused subjects, a blood sample for sCr will be drawn at 48 ± 4 hours. Daily sCr assessments will be recorded up to and including 48 ± 4 hours post surgery. Other post baseline laboratory parameters and Adverse events (AEs) will not be collected for non-transfused subjects. Vital status will be recorded at the time of discontinuation.

The complete list of baseline assessments to be performed pre-operatively on the day before or on the day of surgery before surgery commences are outlined in Table 7.1b.

6.1.2 Acute Transfusion Support Period (Surgery [Day 0] to Post-operative Day 7, Hospital Discharge or Death, Whichever is First)

The complete list of assessments to be performed during the acute transfusion support period are outlined in Table 7.1c.

During the acute transfusion support period (Day 0 to Day 7), hospital discharge or death, whichever is first, patients will be transfused with Test or Control RBCs. Induction and end of anesthesia are considered start and stop time of surgery. All transfusions administered through Day 7 will be of the assigned treatment arm as often as feasible without compromising patient care.

A screen for antibodies specific for INTERCEPT RBCs should be performed every time that a routine IAT is performed during the acute 7-day study transfusion period.

A blood sample for sCr will be taken at $48 (\pm 4$ hours) after completion of surgery, and sCr will be determined on a daily basis during the acute transfusion support period up to 7 days post-surgery. Other parameters will be collected on eCRFs only when available in the medical record.

Randomized subjects who do not receive an RBC transfusion following randomization within the first 48 hours after surgery will be discontinued from the study and replaced.

For non-transfused subjects, a blood sample for sCr will be drawn at 48 ± 4 hours. Daily sCr assessments will be recorded up to and including 48 ± 4 hours post surgery. Other post baseline laboratory parameters and adverse events (AEs) will not be collected for non-transfused subjects. Vital status will be recorded at the time of discontinuation.

Once a subject is randomized, in rare exceptions where study RBCs are unavailable or a subject's need for RBC transfusions exceeds the quantities of the prepared study RBCs (e.g., during a Massive Transfusion Protocol), non-study RBC (conventional) transfusion may be given to provide the subject with an appropriate and necessary treatment. Non-study RBC transfusion data is captured in the eCRF. In this case, a protocol deviation should be noted. Transfusions will be administered according to

Cerus Corporation

Title: A Randomized, Double-Blinded, Controlled, Parallel Group, Non-inferiority, Phase III Study to Evaluate the Efficacy and Safety of the INTERCEPT Blood System for Red Blood Cells in Patients undergoing Complex Cardiac Surgery Procedures (the ReCePI study)

local institutional policy and safety standards as ordered by the medical team for patient care needs. Anesthesia and surgical procedures will be performed according to the local standards of the institution.

Hemodynamic and laboratory results will be recorded daily from post-surgery through post-operative Day 7, hospital discharge or death, whichever occurs first. If an assessment is performed more than once in a day, the first set of results should be entered into the eCRF.

If a subject is discharged prior to the end of the acute transfusion support period (Day 7) but for any reason returns to the study site (e.g., re-hospitalization or standard care) within this acute transfusion support period, lab values routinely collected as standard of care should be recorded in the eCRF.

If multiple assessments (hemodynamic parameters, vital signs, laboratory parameters) are taken in a calendar day, the reported value for first collection of the day should be recorded in the eCRF with the exception of serum creatinine. Serum creatinine will be collected and recorded in the eCRF on a daily basis during the 7 day acute transfusion support period. If serum creatinine is measured multiple times in a day, the worst daily value should be recorded in the eCRF. In addition, a sample to measure sCr will be taken at 48 ± 4 hours after the end of surgery and captured on a specific CRF page for that time-point.

For non-transfused subjects, a blood sample for sCr will be drawn at 48 ± 4 hours hours post-surgery. Serum Creatinine up to and including 48 ± 4 hours post-surgery will be collected.

Urine output (mL/kg/hour) will be recorded in the eCRF daily while a urinary catheter is in place.

Other assessments during this trial period include details related to the specific surgical procedure (type of procedure, start and end times, RBC components transfused, all other blood components transfused, estimated blood loss from the surgical procedure, concomitant medications, intraoperative cell recovery and reinfusion, hemodilution, and nadir temperature). Additionally, daily estimated blood loss from chest tube(s) and from other sources, and day of chest tube removal will be recorded. See Table 7.1c for a detailed list of study assessments.

AEs and SAEs, including TRs and protocol-specified AEs (see Section 7.3), will be assessed from the start of surgery or the start of the first study RBC transfusion (whichever is first) on a daily basis and documented in the eCRF through post-operative Day 7. Adverse events (AEs) will not be collected for non-transfused

Cerus Corporation

Title: A Randomized, Double-Blinded, Controlled, Parallel Group, Non-inferiority, Phase III Study to Evaluate the Efficacy and Safety of the INTERCEPT Blood System for Red Blood Cells in Patients undergoing Complex Cardiac Surgery Procedures (the ReCePI study)

subjects, but vital status will be recorded at the time of discontinuation. See Table 7.1c for a detailed list of study assessments.

NOTE: The following post-operative assessments apply to randomized transfused subjects only.

6.1.3 Post-operative Period (Day 8 [or Post-discharge, if earlier] through Day 28 After Last Study Transfusion)

The complete list of assessments to be performed during this post-operative period are outlined in Table 7.1d.

Laboratory results recorded in the eCRFs during this period will only be those assessed as clinically significant per the Investigator. Following the post-surgery 7-day acute transfusion support period, the post-operative period starts on Day 8 after surgery and goes through the Day 28±3 visit. Subjects will receive conventional non-study RBC components if additional transfusions are needed, as indicated by their treating physician.

Weekly telephone surveillance calls to the subject will be performed to collect AEs, SAEs and TRs. If a surveillance call falls on the same week as the Day 28±3 follow-up visit, the follow-up visit assessments will take precedent and a surveillance call is not required.

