
transfusion using non-study RBC (conventional) may be given to provide the patient with an appropriate and necessary treatment. In this case, a protocol deviation should be documented. If a study RBC transfusion is given after randomization before surgery commences, a protocol deviation should also be documented.
 
Treatment assessments will be divided into an acute transfusion support period starting the day of surgery (Day 0 up to Day 7) during which study RBC (Test or Control) are administered, a post-surgical follow-up period of a minimum of 28 days after the last study transfusion to collect additional safety data, a clinical assessment at day 30 after surgery specifically for mortality and RRT status, and a visit at day 75 (± 15) after the last study transfusion to assess mortality and RRT status, and collect samples for serological screening for antibodies specific to INTERCEPT RBCs.
 
In all patients, anesthesia and surgical procedures will be performed according to the local standards of care. Following the acute transfusion support period, subjects may receive conventional RBC components if additional transfusions are needed, as indicated by their treating physician.
 
Study Assessments: Monitoring and Follow-up
 
Baseline through Acute Transfusion Support Period (Pre-Op Day -1 up to Post-Op Day 7)
 
A screen for antibodies specific for INTERCEPT RBCs should be performed every time that a routine IAT is performed during the acute 7-day study transfusion period.
 
A blood sample for sCr will be taken at 48 ± 4 hours after completion of surgery for both transfused and non-transfused subjects. A sCr will be determined on a daily basis during the acute transfusion support period up to 7 days post-surgery. Other parameters including additional sCr will be collected on eCRFs only when available in the medical record.
 
Randomized subjects who do not receive an RBC transfusion following randomization within the first 48 hours after surgery will be discontinued from the study and replaced.
 
Daily sCr assessments will be recorded up to and including 48 ± 4 hours for transfused and non-transfused subjects. Other post baseline laboratory parameters and adverse events (AEs) will not be collected for non-transfused subjects. Vital status will be reported for randomized and non-transfused subjects at the time of discontinuation.
 
Hemodynamic and laboratory measures will be assessed pre-operatively (Day -1, Baseline) and daily as available in the medical record from post-operative Day 1 through Day 7, hospital discharge or death, whichever occurs first. If a subject is discharged prior to Day 7 but returns to the study site for a standard of care visit on Day 7, blood samples should be obtained on that day for a complete blood count and sCr determination.
 
Hemodynamic parameters that will be collected if available, include heart rate, blood pressure, mean arterial pressure, central venous pressure (CVP), and peripheral oxygen saturation via pulse oximetry probe.
				

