4 INVESTIGATIONAL PLAN

4.1 ENDPOINTS

4.1.1 Primary Endpoints

The primary efficacy endpoint is the proportion of patients, who have received at least one study transfusion with a diagnosis of renal impairment defined as:

- Any raised sCr level, occurring after transfusion of a study RBC, of ≥ 0.3 mg/dL (or 26.5 μ mol/L) from the pre-surgery baseline within 48 ± 4 hours of the end of surgery.

If any subject meets this criterion before receiving a study transfusion, that particular event will not be included in the primary endpoint analysis. The treatment comparison for the primary efficacy endpoint will be assessed by a non-inferiority test (Test–Control) with a non-inferiority margin of 50% increase from the Control rate and two-sided 0.05 alpha level. Patients who receive a study transfusion but die within 48 hours after surgery will be included in the mITT analysis but excluded from the per protocol analysis.

The primary safety endpoints are:

- Proportion of patients with any treatment-emergent adverse events (TEAEs) possibly, probably or definitely related to study RBC transfusion through 28 days after the last study transfusion; and
- Proportion of patients with treatment-emergent antibodies with confirmed specificity to INTERCEPT RBCs by end of study (i.e., 75 ± 15 days after the last study transfusion).

TEAEs by definition will comprise all untoward medical events occurring after the start of the first study RBC transfusion and during the study (i.e., adverse events, serious adverse events, unanticipated adverse device effects, TRs and within 28 days post last study RBC transfusion). The primary safety endpoint is focused on possibly, probably or definitely related adverse events to the study RBC transfusion, because these patients have many adverse events which are unrelated to study RBC transfusion.

Cerus Corporation

Title: A Randomized, Double-Blinded, Controlled, Parallel Group, Non-inferiority, Phase III Study to Evaluate the Efficacy and Safety of the INTERCEPT Blood System for Red Blood Cells in Patients undergoing Complex Cardiac Surgery Procedures (the ReCePI study)

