8.1.2 Safety Analyses

Treatment- emergent AEs (defined as AEs with an onset date/time that is on or after the start date/time of the first study transfusion) will be summarized by treatment group, system organ class (SOC), and preferred term. Descriptive summaries of safety measures will be based on observed data. No imputation of missing scores will be implemented.

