8.2 DETERMINATION OF SAMPLE SIZE

A total of at least 292 transfused subjects, approximately 146 per arm, are planned to generate sufficient efficacy and safety data for the Test and Control components in patients undergoing cardiac surgery procedures.

For the primary efficacy endpoint, a non-inferiority test will be conducted to assess for treatment difference (Test – Control). By assuming the proportion of patients with $\Delta sCr \geq 0.3\text{mg/dL}$ to be 30% in the Control arm and no more than 50% increase from the Control rate as the non-inferiority margin, a sample size of 292 patients (146 per arm) will provide approximately 80% power to declare non-inferiority at the two-sided 0.05 alpha level, assuming the true treatment difference is zero.

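### Keeping only the worst creatinine of each calendar day does not match the clock-time window of the primary endpoint and can miss a qualifying value in two limited situations

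*Protocol*

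**What the plan says.** **Endpoint.** Section 4.1.1 counts "Any raised sCr level, occurring after transfusion of a study RBC" if it is at least 0.3 mg/dL above the pre-surgery baseline and within 48±4 hours of the end of surgery. It adds: "If any subject meets this criterion before receiving a study transfusion, that particular event will not be included in the primary endpoint analysis".

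**Recording rule.** Section 6.1.2 asks for daily sCr through the seven-day support period and then says: "If serum creatinine is measured multiple times in a day, the worst daily value should be recorded in the eCRF". Table 7.2 footnote f repeats this. In the table the footnote is attached to the creatinine cell for Days 1–7, not to the Day 0 cell.

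**Separate sample.** Section 6.1.2 continues: "In addition, a sample to measure sCr will be taken at 48 ± 4 hours after the end of surgery". That result has its own CRF page and lies outside the worst-of-day rule.

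**Synopsis.** Under Study Assessments it says: "Other parameters including additional sCr will be collected on eCRFs only when available in the medical record". The parallel sentences in Sections 6.1.2 and 7.1 do not mention additional sCr.

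**The concern.** The endpoint window opens at a transfusion time and closes at a fixed number of hours after surgery. Neither boundary falls at midnight, yet the recording rule works by calendar day and selects by size alone. On a day that contains a boundary, the largest value can lie outside the window while a smaller value inside it also reaches 0.3 mg/dL. Followed literally, the rule leaves the smaller value out of the database.

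This touches the only primary efficacy endpoint. Section 8.1.1 sets the margin as half the observed Control rate, so lost events lower the rates and shrink the absolute margin with them. The synopsis also points sites to a different practice, so sites could collect sCr differently.

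**Working it through.** **1. The plan's own figure.** Section 8.2 assumes the event rate "to be 30% in the Control arm", with "no more than 50% increase from the Control rate as the non-inferiority margin", a true difference of zero and two-sided alpha of 0.05.

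- Margin: 0.5 × 0.30 = 0.15.
- n per arm = (1.960 + 0.842)² × 2 × 0.30 × 0.70 / 0.15² ≈ 147, or 294 in total.
- At 146 per arm: SE = √(2 × 0.30 × 0.70 / 146) = 0.0536, and power = Φ(0.15/0.0536 − 1.960) = 79.9%.

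The stated 292 and approximately 80% reproduce. The sample size does not depend on the recording rule.

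**2. Start of the window.** Take the day of first study transfusion, with one sCr before and one after it, both within 52 hours. Express each as the rise over baseline in mg/dL.

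| Before | After | Value kept | Consequence |
|---|---|---|---|
| <0.3 | <0.3 | either | no event either way |
| <0.3 | ≥0.3 | after | event kept |
| ≥0.3 | ≥0.3 and higher | after | event kept |
| ≥0.3 | ≥0.3, equal or lower | before (either, if tied) | qualifying later value can be lost |
| ≥0.3 | <0.3 | before | rightly excluded if timed, wrongly counted if not |

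Only the fourth row loses a value. Going through all 196 pairs of rises from −0.3 to 1.0 in steps of 0.1 gives the same result: the 48 pairs in the second row are all kept. These are counts of combinations, not patient frequencies. Section 4.3 allows the first study transfusion up to 48 hours after surgery, so the day concerned may be Day 0, 1 or 2.

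**3. End of the window.** Read the limit as 48 + 4 = 52 hours. As a constructed example, let surgery end at 10:00 on Day 0, so the window closes at 14:00 on Day 2. The subject has already been transfused and has no earlier rise of 0.3.

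- 06:00, 44 h: dedicated sample, rise 0.2.
- 12:00, 50 h: routine draw, rise 0.3, which qualifies.
- 20:00, 58 h: routine draw, rise 0.4, out of window.

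The daily record keeps 0.4 and the 48-hour page shows 0.2. The qualifying 0.3 is not recorded, although this subject never met the criterion before transfusion.

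**4. What limits the loss.** In both situations, any other recorded value of at least 0.3 that is post-transfusion and in-window still shows the event. That includes the 48-hour sample. On days lying wholly between the first transfusion and 52 hours, the worst value is the right one for an endpoint of this kind.

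**5. Draw times.** The protocol does not say whether the draw time of the worst value is captured. Transfusion time is available, because Section 8.1.2 defines treatment emergence by "onset date/time that is on or after the start date/time of the first study transfusion". If draw times were missing, the fifth row above and post-window values on Day 2 could be counted wrongly.

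**6. Scale of the effect.** The protocol gives no rate of repeat draws, no distribution of first-transfusion times and no share of affected subjects. Purely as an assumption, let a share L of true events be lost equally in both arms. Put p = 0.30 × (1 − L) and margin 0.5p into the power formula of step 1:

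| L | p | Power at 146 per arm |
|---|---|---|
| 0 | 0.300 | 79.9% |
| 2% | 0.294 | 78.7% |
| 5% | 0.285 | about 77% |
| 10% | 0.270 | 73.8% |

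Nothing in the protocol says which row, if any, applies.

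**The case against.** **The rule rarely loses anything.** Table 7.2 footnote h asks for AKI-related assessments at about the same time each day, so one regular draw is the norm. The Day 2 route needs three things together: a qualifying in-window value, a still higher value after 52 hours that day, and no other recorded qualifying value. It narrows as surgery ends later: an end at 15:00 closes the window at 19:00 on Day 2, and from 20:00 onward no part of Day 2 lies outside it. This stands, and it is why the point is limited.

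**The displaced value may not be an event at all.** A raised level that persists from before transfusion could be the very event that Section 4.1.1 excludes. The wording can also be read the other way, since it excludes that event and not the subject. The protocol leaves this open, and the classification needs stating.

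**Draw times may well be captured.** eCRF fields are not laid out in the protocol, and Section 5.3.1 mentions CRF completion guidelines. This also stands. A reader might infer that a rise after transfusion cannot be identified at all. The document does not support that, because a timed worst value can be ordered against the transfusion.

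**The synopsis already solves it.** It would largely do so if it governs, but Section 6.1.2 and footnote f say otherwise, so the conflict remains.

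**Conclusion.** The mismatch is real but narrow. As written, the rule can miss a qualifying value in two situations: on the first-transfusion day, when the subject was already at 0.3 mg/dL or more beforehand and the later value is no higher; and on Day 2, when a higher post-window value displaces a qualifying one and the 48-hour sample is below threshold. The first matters only if such a subject can still count. Both assume that sites follow Section 6.1.2 and not the synopsis.

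Two stronger inferences are tempting and do not hold. One is that same-day post-transfusion events in general are lost; a new rise after transfusion is that day's worst value, so it is kept unless a later out-of-window value exceeds it. The other is a definite fall in power, for example to about 70%. An unstratified simulation of the planned rule, with the margin taken from the observed Control rate, gives 74.6% with no loss and 69.5% with 10% loss. The 10% has no basis in the protocol, and the gap between 80% and 74.6% comes from estimating the margin, which is a separate matter. Equal proportional loss in both arms leaves the rate ratio unchanged, so it costs power but does not favour non-inferiority. Without draw times the error could instead raise the rates and widen the absolute margin.

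**What to change.** - In Section 6.1.2 and Table 7.2 footnote f, record each available sCr with draw date and time from baseline to 52 hours after the end of surgery. At minimum, on the first-transfusion day and Day 2, also record the worst value that is both post-transfusion and in-window.
- Derive the daily worst value by program for the KDIGO endpoint (Section 7.3.1.6).
- Align the synopsis, Sections 6.1.2 and 7.1, and Table 7.2 on whether additional sCr values are entered, and make clear that the rule covers Day 0.
- State in Section 4.1.1 whether a subject who met the criterion before transfusion can still count through a later post-transfusion value.
- For completed subjects, limit chart retrieval to those with several draws on the first-transfusion day or Day 2.

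The cost is an eCRF change, some extra data entry and source verification. No new blood draws are needed.
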